Title: Comparison of Lesion Sterilization and Tissue Repair
Technique With Conventional Pulpectomy in the Treatment of
Pulpal Lesions in Primary Molars in Children

Unique Protocol ID : B.30.2.ATA.0.01.00/477

NCT Number : NCT07026435

Date : May 28, 2026

Document Type: Study Protocol and Statistical Analysis Plan

Study Protocol and Statistical Analysis Plan

This study will be carried out in the Department of Pediatric Dentistry of Atatürk University and pediatric patients between the ages of 4-10 who need endodontic treatment in primary molars I and II will be included in the study.

Inclusion Criteria

A. The criteria for inclusion in the study group are as follows:

1. Clinically and radiographically diagnosed with a pulpal lesion,
2. Inability to perform traditional pulpectomy treatment due to pathological or physiological root resorption exceeding 2/3 rate,
3. Not having a systemic disease,
4. No history of allergies (against antibiotics),
5. The patient and their parents agree to come to routine dentist check-ups and participate in the study, and
6. It is the refusal of the child and/or family to accept tooth extraction.

B. The criteria for inclusion in the study in the control group are as follows:

1. Clinically and radiographically diagnosed with a pulpal lesion,
2. Teeth that do not have pathological resorption and have physiological root resorption not exceeding 2/3 or have a traditional pulpectomy indication without physiological resorption,
3. Not having a systemic disease and
4. It is the agreement of the patient and their parents to come to routine dentist check-ups and participate in the study.

Exclusion Criteria

A. The study exclusion criteria in the study group are:

1. Those with systemic diseases,
2. Those who do not give the necessary consent for participation in the study, and
3. They are those who are allergic to antibiotics or other drugs.

B. In the control group, the study exclusion criteria were:

1. Those with systemic diseases,
 2. Those who do not give the necessary consent for participation in the study, and
- They are those who are allergic to antibiotics or other drugs.

Ethics Committee Approval

For our study, ethics committee approval was obtained with the letter "Atatürk University Faculty of Medicine Clinical Research Ethics Committee 12.07.2024 / Meeting number B.30.2.ATA.0.01.00 / Decision No: 477".

Sample Size:

It is planned to investigate the relationships between measurements in the main hypotheses of the research. Similar studies that can be used in the calculation of sample size were examined and the sample size calculation, which gives the highest number according to the statistical methods to be applied in line with the main hypotheses, was taken into account. In this study, using the program "G. Power-3.1.9.2" (Faul, F., Erdfelder et al. (2009)), at the 95% confidence level ($\alpha=0.05$), the standardized effect size was 0.4423 (Doneria, D., et al. (2017), Table 3; 6th month) (s.d.: 6) and the minimum sample size was obtained as 70 with a theoretical power of 0.80.

30% of the sample size (21 observations) was added to the study, which was calculated by taking into account the probability of observation loss over time. The minimum sample size for each time was calculated as 91. (Doneria et al., 2017; Faul et al., 2009)

The result of the analysis is as follows.

χ^2 tests - Goodness-of-fit tests: Contingency tables

Analysis: A priori: Compute required sample size

Input: Effect size w = 0.4423761

α err prob = 0.05

Power (1- β err prob) = 0.80

Df = 6

Output: Noncentrality parameter λ = 13.6987630

Critical χ^2 = 12.5915872

Total sample size = 70

Actual power = 0.8025413

Treatment Protocol

This controlled clinical trial included a comparison of the LSTR method with conventional pulpectomy in pulp lesions in primary molar teeth. The study involved 110 primary molar teeth and was divided into two groups: 55 with LSTR and 55 with conventional pulpectomy. In the LSTR group, 28 teeth will be covered with stainless steel crowns and 27 teeth will be restored with Compomer fillings. Likewise, in the traditional pulpectomy group, 28 teeth will be covered with a stainless steel crown and 27 teeth will be restored with a Compomer filling. Stainless steel crown and Compomer restoration teeth was determined according to the patient's compatibility status and the wishes of the parents/children.

Table

Working Group (LSTR)			Control Group (Pulpectomy)	
Restoration	Compomer	SSC	Compomer	SSC
Number of Teeth	27	28	27	28
Total	55		55	

LSTR Group (Study Group): After local anesthesia is provided, rubber dam insulation will be made. The entrance cavity will be prepared using the #4 round bur and the necrotic tissue will be removed. Then, irrigation with saline and sodium hypochlorite will be performed. A cavity will be prepared for antibiotic paste with a depth of 2mm and a width of 1mm with a #4 tungsten carbide round bur at the channel mouths. If there is bleeding, a cotton pellet moistened with 5% sodium hypochlorite, which is an effective hemostatic agent, will be kept in the pulp chamber to stop the bleeding. 35% phosphoric acid was applied for 15 seconds to remove the smear layer, then the cavity will be washed and dried with saline. Since ciprofloxacin 500 mg antibiotic tablets are enteric-coated, their enteric coating will be completely scraped off with a scalpel and then pulverized in a clean mortar and stored in a moisture-free environment in glass bottles that do not receive light. The powder form of metronidazole is available on the market. In order to gain radioopacity of the powder (metronidazole and ciprofloxacin) prepared from a mixture of two antibiotics, it will be mixed with primary tooth canal filling material (Calcium Hydroxide Paste with Iodofome) (Viopex-Spident-Korea) to give a paste consistency. Antibiotic powders will be available in individual containers and the powders will be mixed with Viopex in the determined proportions (1:1) just before the application and the paste will be prepared freshly. Then, after the cavity is dried, the prepared pulp is placed in its cavity and covered with a light-curing, ready-to-use glass ionomer composite base cement (Ionoseal-VOCO-Germany) and the thread will be

restored with a stainless steel crown (Icrown-Seil Global-Korea) or composite filling (Twinky star-VOCO-Germany) (Picture 1). The upper restoration will be determined according to the child's adaptation status. (Stainless steel crown will be performed in children treated under general anesthesia, and composite restoration will be performed in children treated in routine dental clinics.) In case of swelling and lymphadenopathy in the tooth, additional systemic antibiotics will also be prescribed.

Pulpectomy Group (Control Group): Traditional pulpectomy treatment will be applied. Local anesthesia will be applied to the lesion area and the cavity will be opened. The pulp tissue will be removed and after the canals are cleaned and irrigated, the primary tooth will be filled with canal paste (Calcium Hydroxide Paste with Iodofome) (Viopex-Spident-Korea). After the pulp chamber is sealed with a light-curing, ready-to-use glass ionomer composite base cement (Ionoseal-VOCO-Germany), the upper restoration will be done with a stainless steel crown (Icrown-Seil Global-Korea) or compound filling (Twinky star-VOCO-Germany) (Figure 2).

Clinical evaluations of the teeth in both the study and control groups will be performed at 3 months, 6 months and 1 year, and radiographic evaluations will be made at 6 and 12 months. These evaluations are necessary to monitor the effectiveness and course of treatment.

Evaluation Criteria in Follow ups

The effectiveness of the treatment will be evaluated on the following criteria:

- √ Relief of clinical symptoms (pain, swelling, etc.).
- √ Radiographically the state of healing of the lesion.
- √ In post-treatment follow-ups (3rd month, 6th month). Month and 12 Months) the status of lesion sterilization and tissue repair.

- √ Cessation of existing pathological root resorption (internal or external)
- √ Continuation of physiological root resorption in accordance with the age of the child.

Statistical & Analytical Methods:

The data obtained from our study will be entered into the Microsoft Excel program. Afterwards, necessary analyzes will be made with the IBM SPSS 20 statistical analysis program. Survival analyzes of the teeth participating in the study will be made according to months.

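### No tooth is eligible for both groups, so an LSTR-versus-pulpectomy difference, or the lack of one, cannot be attributed to technique

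*Combined protocol and SAP*

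**What the plan says.** The title announces a comparison of the two techniques, and Treatment Protocol repeats it: "This controlled clinical trial included a comparison of the LSTR method with conventional pulpectomy in pulp lesions in primary molar teeth". On how the groups are formed, that section says only: "The study involved 110 primary molar teeth and was divided into two groups: 55 with LSTR and 55 with conventional pulpectomy". No randomisation, matching or stratification is described.

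The groups have separate entry criteria.

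- Inclusion Criteria, A (study group), item 2: "Inability to perform traditional pulpectomy treatment due to pathological or physiological root resorption exceeding 2/3 rate".
- Inclusion Criteria, A, item 6, with no counterpart for controls: "It is the refusal of the child and/or family to accept tooth extraction".
- Inclusion Criteria, B (control group), item 2: "Teeth that do not have pathological resorption and have physiological root resorption not exceeding 2/3 or have a traditional pulpectomy indication without physiological resorption".

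Statistical & Analytical Methods names one analysis, tooth survival by month, and no covariates. Evaluation Criteria in Follow ups lists five criteria. Two of them concern resorption: whether pathological resorption present at entry has stopped, and whether physiological resorption proceeds as expected for age. No section mentions that the groups differ by design or limits how a difference between them may be read.

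**The concern.** Most non-randomised comparisons have some overlap: at least some patients could have received either treatment, and adjustment or matching can draw on them. Here the entry criteria appear to remove that overlap. If they do, a difference in outcome may come from the technique, from the resorption that decided the technique, or from both, and the data cannot say which. The same holds if no difference is found.

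The question in the title would then have no answer from this study, whatever its size. A reader who takes the word comparison at face value could draw a conclusion about relative efficacy that the design does not support.

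**Working it through.** **1. Do the criteria overlap?** The wording of A.2 and B.2 is loose, so each reading is checked.

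| Reading | LSTR tooth (A.2) | Control tooth (B.2) | Overlap |
|---|---|---|---|
| The 2/3 limit in A.2 applies to both types of resorption | Pulpectomy not possible; either type above 2/3 | First branch: no pathological resorption, physiological not above 2/3 | None |
| The 2/3 limit applies to physiological resorption only | Pulpectomy not possible; pathological resorption, or physiological above 2/3 | First branch, as above | None |
| Either reading, with B.2's second branch admitting some pathological resorption | Pulpectomy not possible | Pulpectomy indicated, no physiological resorption | None |

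In the first two rows resorption separates the groups. In the third, feasibility of pulpectomy does. Every reading gives disjoint groups.

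**2. What follows for estimation.** Write D for the expected difference in success, LSTR minus control, T for the technique effect and I for the effect of having a different indication. Then D = T + I. The data estimate D only. Separating T from I needs teeth that could have received either technique, and there are none. An adjusted estimate would be extrapolation, and a larger sample only estimates T + I more precisely.

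**3. The plan's own figure.** Under Sample Size, w = 0.4423761, df = 6 and alpha = 0.05. With N = 70, lambda = 70 × 0.4423761² = 13.6988. The critical chi-square is 12.5916 and power is 0.8025, as printed; 70 × 1.30 = 91 also agrees. The arithmetic reproduces, but it concerns random error and does not bear on this point.

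**4. Illustration of size.** The documents give no success rates by resorption, so the rates below are assumptions. Take T = 0, n = 55 per group, 90% success in control teeth, and a two-sided 5% pooled two-proportion z test. With p̄ the mean of the two rates,

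P(reject) ≈ Φ[(d − 1.96·s0)/s1], where s0 = √(2p̄(1 − p̄)/n) and s1 = √((p1(1 − p1) + p2(1 − p2))/n).

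For 90% v 80%: d = 0.10, s0 = √(2 × 0.85 × 0.15/55) = 0.0681, s1 = √((0.09 + 0.16)/55) = 0.0674. This gives Φ[(0.10 − 0.1335)/0.0674] = Φ(−0.50) = 0.31.

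| Assumed LSTR success | Formula | Exact binomial enumeration, z test | Same, Fisher's exact test |
|---|---|---|---|
| 85% | 0.12 | 0.12 | 0.07 |
| 80% | 0.31 | 0.31 | 0.22 |
| 75% | 0.54 | 0.56 | 0.45 |

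With equal rates of 90% the z test rejects in 5%, as it should.

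**5. The reverse error.** If T = +10 points and I = −10 points, D = 0. Success is 90% in both groups, and the z test rejects in only 5% of trials although the technique effect is real.

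**6. The outcome list.** A control tooth entered without pathological resorption can neither meet nor fail the criterion that existing pathological resorption has stopped. A success measure using all five criteria would therefore mean different things in the two groups.

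**The case against.** **The groups follow clinical indication, and the plan claims no randomisation.** Both are true. Controlled does not mean randomised, and which teeth suit which technique is not in question here. This defends the allocation but does not make the groups comparable.

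**A contrast confined to teeth near the 2/3 limit might be informative.** It would need a measured degree of resorption and a planned method. The documents give neither.

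**The rejection rates are invented and depend on a test the plan does not name.** This stands. The plan sizes the study with a chi-square test and otherwise names only survival analyses. The rates are simply the power of the chosen test at assumed gaps, and Fisher's exact test gives lower ones. They show that the problem can be material; they are not this trial's error rate.

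A reader might also infer more than the documents support:

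- *That LSTR teeth are the worse teeth, so the bias runs against LSTR.* A.2 also admits physiological resorption, which Evaluation Criteria in Follow ups treats as normal for age. No prognosis by resorption is given.
- *That systemic antibiotics are a co-treatment for LSTR only.* The statement "additional systemic antibiotics will also be prescribed" stands in the LSTR text and depends on swelling and lymphadenopathy. The shorter pulpectomy text is silent, which does not show that controls go without.
- *That the plan intends to claim equivalence.* It states no non-inferiority aim or decision rule and mentions main hypotheses without listing them.

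**Conclusion.** The point holds. On every reading of A.2 and B.2 the groups are disjoint, so technique is fully determined by resorption and feasibility of pulpectomy, and the required refusal of extraction adds a further difference. No analysis of these data can attribute a between-group difference, or its absence, to technique. That conclusion rests on the entry criteria alone and needs no assumption about success rates.

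The direction and size of the bias are unknown. Under the stated assumptions a false difference would appear in about 12% to 56% of trials with the z test (7% to 45% with Fisher's exact test), and a real effect could equally be masked. The design can support a description of how each technique performs within its own indication. The title and Treatment Protocol go further than that and need correcting before the results are interpreted.

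**What to change.** Keep the groups and the treatments, and change what the study claims.

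1. In the title or objective, Treatment Protocol and Statistical & Analytical Methods, state that the groups have different, non-overlapping indications. State that any between-group contrast, including survival by month, is descriptive, and that neither superiority, equivalence nor inferiority of LSTR to pulpectomy will be concluded.
2. Make the main result the 12-month success proportion and the planned survival estimate within each group, with 95% confidence intervals. Define success by criteria that teeth in that group can meet or fail.
3. Let the intervals allow for several teeth per child, since the plan counts teeth and sets no limit of one per child. At 55 teeth and an assumed 80% to 90% success, Wilson half-widths are about 8 to 10 points if teeth are independent, and about 9 to 13 points with an assumed design effect of 1.3 to 1.5.
4. Tabulate by group the type and degree of resorption, age, tooth type, restoration and systemic antibiotic use, recording antibiotic use in both groups.

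Neither a ban on p values nor renaming the study as cohorts is needed once the contrast is labelled descriptive. The cost is a less ambitious claim and slightly more baseline recording: eligibility needs only a judgement against the 2/3 limit, so degree of resorption is an extra item. No new patients or procedures are required.

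### The stated 0.80 power belongs to a 6-df contingency chi-square that matches neither the two-group design nor the named survival analysis, so power for the trial's own comparison is not established

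*Combined protocol and SAP*

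**What the plan says.** The Sample Size section says the calculation was chosen to fit the methods serving the main hypotheses, taking whichever gave the largest number. It concludes that "the minimum sample size was obtained as 70 with a theoretical power of 0.80". The software output beneath identifies the procedure as "χ^2 tests - Goodness-of-fit tests: Contingency tables". Its inputs are "Effect size w = 0.4423761", "α err prob = 0.05", "Power (1- β err prob) = 0.80" and 6 degrees of freedom. Its outputs are "Noncentrality parameter λ = 13.6987630" and "Total sample size = 70". The effect size comes from the month-6 results in a table of a cited study. Adding 30% for losses takes 70 to 91.

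The Treatment Protocol section then plans 110 teeth: 55 for lesion sterilization and tissue repair (LSTR) and 55 for pulpectomy, each split 27/28 by type of restoration.

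The Statistical & Analytical Methods section names one analysis: "Survival analyzes of the teeth participating in the study will be made according to months". Beyond that it mentions only unspecified further analyses in SPSS. It gives no event definition, test, group contrast, primary time point, expected success rate or expected number of failures.

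**The concern.** A comparison of two groups on success or failure, or by a log-rank test, has 1 degree of freedom. A table with two groups reaches 6 df only if the outcome has seven categories. The four group-by-restoration cells reach it only with a three-category outcome, since (4 − 1)(3 − 1) = 6. The plan defines neither outcome and does not say which table it had in mind. The one power figure in the plan therefore belongs to a test that the plan does not name.

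What is at stake is interpretation. LSTR is set against a conventional treatment. A reader told that power is 0.80, with no indication of the difference this refers to, could take a non-significant result as evidence that the two perform alike. The value w = 0.44 gives no sense of how large a difference in success it represents.

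**Working it through.** **1. The plan's own figure.** Inputs from the Sample Size section: w = 0.4423761, α = 0.05, df = 6, N = 70.
- λ = N·w² = 70 × 0.4423761² = 13.699.
- The critical value of χ² on 6 df at 0.05 is 12.592.
- Power = P(noncentral χ²(6, λ) > 12.592) = 0.8025. At N = 69 it is 0.796, so 70 is the smallest N.

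The output reproduces exactly.

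**2. Same w, with the test changed to 1 df.** Power = P(noncentral χ²(1, N·w²) > 3.841).

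| Teeth | λ = N·w² | Power, 6 df | Power, 1 df |
|---|---|---|---|
| 70 | 13.70 | 0.803 | 0.959 |
| 77 | 15.07 | 0.845 | 0.973 |
| 110 | 21.53 | 0.957 | 0.996 |

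At this w, 80% power needs 41 teeth on 1 df against 70 on 6 df. The 77 is 110 × 0.70, an assumed 30% loss from the planned 110.

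**3. What w = 0.4424 means in two equal groups.** For success proportions p₁ and p₂ with mean m, w = |p₁ − p₂| / (2√(m(1 − m))).
- p₁ = 0.95 gives p₂ = 0.573: 0.377 / (2√(0.7615 × 0.2385)) = 0.442.
- p₁ = 0.90 gives p₂ = 0.493: 0.407 / (2√(0.6965 × 0.3035)) = 0.443.

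The differences are about 38 and 41 points. The 95% and 90% are assumptions; the documents give no success rates.

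**4. Difference detectable with about 80% power, two-sided 5%, 1 df.** Power = Φ[(|p₁ − p₂| − 1.96·SE₀)/SE₁], with SE₀ = √(2m(1 − m)/n), SE₁ = √([p₁(1 − p₁) + p₂(1 − p₂)]/n) and n teeth per group. The 95% confidence interval half-width is 1.96·SE₁.

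Example, 90% v 68% with n = 55: SE₀ = √(2 × 0.79 × 0.21/55) = 0.0777; SE₁ = √((0.09 + 0.2176)/55) = 0.0748; power = Φ[(0.22 − 0.1522)/0.0748] = Φ(0.906) = 0.82; half-width = 14.7 points.

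| Evaluable teeth | Assumed success | Difference | Power | 95% CI half-width |
|---|---|---|---|---|
| 110 (n = 55) | 95% v 76% | 19 points | 0.82 | 12.7 points |
| 110 (n = 55) | 90% v 68% | 22 points | 0.82 | 14.7 points |
| 77 (n = 38.5) | 95% v 71% | 24 points | 0.81 | 15.9 points |
| 77 (n = 38.5) | 90% v 63% | 27 points | 0.81 | 18.0 points |

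**5. Smaller differences, also assumed.** For 90% v 75%, power is 0.54 at 110 teeth and 0.41 at 77. For 90% v 80%, it is 0.31 and 0.23.

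**6. Log-rank equivalent.** Schoenfeld's approximation is power = Φ(√d·|ln HR|/2 − 1.96), with d failures and HR = ln p₂/ln p₁.
- 90% v 80% at 110 teeth: d = 55 × (0.10 + 0.20) = 16.5, HR = 2.12, power 0.33.
- 90% v 70% at 110 teeth: d = 55 × (0.10 + 0.30) = 22, HR = 3.39, power 0.82.
- With 77 teeth the two become 0.25 and 0.67.

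The survival version tells much the same story as the two-proportion version.

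**The case against.** A reader might infer that the trial lacks the power it states, or is underpowered. The documents do not support that. Changing only the test, at the plan's own effect size, raises power, and the planned 110 teeth exceed both 70 and 91. Every figure below 80% in the working depends on success rates that the documents do not give. The plan sets no clinically important difference, and whether w = 0.44 is realistic depends on the cited study's table, which was not available for this review. All of this stands.

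It is also fair to say that the plan does not commit to a two-group log-rank test. Its mention of further analyses leaves contingency tests possible, and a table of four cells by three outcomes would give 6 df. That possibility does not rescue the statement, because a test that is not named cannot carry a power claim. If it is the intended test, the remedy is to say so.

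Two further points limit the concern. The 77-tooth figures are a cautious case: adding 21 teeth to 70 allows for a loss of 21/91 = 23%, which would leave about 85 of 110, and in a survival analysis lost teeth contribute until they are censored. The month-6 source of the effect size is not a fault in itself, since six months is a scheduled assessment and the plan applies its minimum at each time.

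Finally, nothing in the plan says that non-significance will be read as equivalence. The proposed sentence on this is a safeguard and does not correct anything written.

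**Conclusion.** The concern holds as a mismatch between the power statement and the comparison. The 0.80 at 70 teeth is correct for a 6-df contingency chi-square at w = 0.4424. That test fits neither the two-group design nor the only named analysis, so the figure is not the power of the comparison the trial makes. No shortfall has been demonstrated: power may be above or below 0.80 depending on the true difference.

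What the plan leaves undisclosed is how large an effect the figure rests on, about 38 to 41 points in a two-group success/failure comparison. On 1 df, the planned enrolment detects about 19 to 22 points with 80% power if every tooth is evaluable, and about 24 to 27 points at 77 teeth. These figures assume 95% or 90% success in the better group, equal groups, independent teeth and a two-sided 5% level; the 77 also assumes a 30% loss.

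**What to change.** Rewrite the power paragraph in the Sample Size section.

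- Replace the 6-df statement with one for the two-group comparison actually planned (1 df or log-rank). Use the endpoint and time point the sponsor chooses, with its assumed success rates or number of failures. Alternatively, keep the 6 df and name the table, outcome categories and test that produce it.
- State the difference detectable with 80% power. On the assumptions used here this is about 19 to 22 points with all 110 teeth evaluable (95% v 76%, 90% v 68%), or about 24 to 27 points at 77 teeth (95% v 71%, 90% v 63%).
- State the matching 95% confidence interval half-widths: about 13 to 15 points at 110 teeth and 16 to 18 at 77.
- Label every success rate and the loss fraction as assumptions.
- Name the same test in the Statistical & Analytical Methods section, and add that a non-significant result will not be reported as equivalence.

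Which endpoint and time point to use is for the sponsor to decide. The cost is a rewritten paragraph, a line in the methods section and a power statement that looks less favourable for smaller differences. No additional enrolment is involved.

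### Systemic antibiotics for swelling with lymphadenopathy are written into the LSTR arm only and without timing, although relief of swelling is scored in both arms

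*Combined protocol and SAP*

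**What the plan says.** All references are to the combined protocol and SAP.

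- **Treatment Protocol, LSTR Group.** The last sentence of the procedure reads "In case of swelling and lymphadenopathy in the tooth, additional systemic antibiotics will also be prescribed". It gives no time point and no rule for recording use.
- **Treatment Protocol, Pulpectomy Group.** The description opens with "Pulpectomy Group (Control Group): Traditional pulpectomy treatment will be applied" and runs from anaesthesia to the final restoration without mentioning systemic antibiotics.
- **Follow-up schedule.** "Clinical evaluations of the teeth in both the study and control groups will be performed at 3 months, 6 months and 1 year". Radiographs are assessed at 6 and 12 months.
- **Evaluation Criteria in Follow ups.** The first criterion is "Relief of clinical symptoms (pain, swelling, etc", an open-ended list that names swelling.
- **Statistical & Analytical Methods.** The only analysis named is "Survival analyzes of the teeth participating in the study will be made according to months". No failure event is defined, and nothing is said about teeth whose patients received systemic antibiotics.
- **Exclusion Criteria.** Both groups carry the same item: "They are those who are allergic to antibiotics or other drugs".

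**The concern.** The finding that triggers the antibiotic in the LSTR arm includes a sign that is later used to judge whether treatment worked. If the provision is applied in one arm only, the clinical comparison no longer isolates the local procedure, and the plan has no means of separating the two effects afterwards. The LSTR paste itself contains two antibiotics, so a systemic antibiotic overlaps with the mechanism under test. Use that is not recorded prospectively may not be recoverable later. At stake is the interpretation of the clinical effectiveness criterion.

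**Working it through.** **1. The two arms side by side**

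| Item | LSTR | Pulpectomy |
|---|---|---|
| Provision for systemic antibiotics | Yes, for swelling and lymphadenopathy | None stated |
| Timing of provision | Not stated | – |
| Relief of swelling scored | Yes | Yes |
| Clinical visits | 3, 6, 12 months | 3, 6, 12 months |
| Antibiotic use recorded or analysed | Not stated | Not stated |
| Antibiotic allergy excluded | Yes | Yes |

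The only stated difference in concomitant treatment is in the first row, and it concerns a sign that is scored in both arms.

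**2. What follows under each reading of the timing**

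- *Treatment visit.* A swollen tooth receives the paste and a systemic drug together. Relief recorded at the first clinical visit, at 3 months, is attributed to LSTR. This is a baseline co-intervention. The documents do not establish how much of its effect lasts to 3–12 months.
- *Follow-up.* Clinical visits are 3 to 6 months apart. A swelling that appears and is treated between visits can be absent at the next one. With no failure event defined, nothing makes that tooth a failure.

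**3. Can the size be derived?**

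The plan has no figure on this point. Its one calculation, under Sample Size, reproduces: λ = N × w² = 70 × 0.4423761² = 13.6988; the critical χ² on 6 degrees of freedom is 12.5916; power is 0.8025 (69 teeth give 0.7958). That calculation uses a standardised effect size, so it supplies no failure rate for either arm and no rate of antibiotic use. The bias therefore cannot be computed from the documents.

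**4. Illustration of the follow-up reading only (all rates are assumptions)**

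Input from the plan: "divided into two groups: 55 with LSTR and 55 with conventional pulpectomy". Let m be the share of LSTR failures that go unscored. Then

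observed LSTR failure = true LSTR failure × (1 − m).

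Power is for a two-sided 5% comparison of two proportions (normal approximation), with 55 independent teeth per arm and no losses.

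Assumed true failure of 30% with LSTR and 10% with pulpectomy:

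| m | Observed LSTR failure | Difference (points) | Power |
|---|---|---|---|
| 0 | 30% | 20 | 0.753 |
| 0.10 | 27% | 17 | 0.635 |
| 0.25 | 22.5% | 12.5 | 0.426 |
| 0.50 | 15% | 5 | 0.121 |

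Assumed equal true failure of 20%: m = 0 gives no distortion; m = 0.10 gives 20 − 18 = 2 points in favour of LSTR; m = 0.25 gives 20 − 15 = 5 points; m = 0.50 gives 20 − 10 = 10 points.

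The range includes zero. The tables show how sensitive the comparison would be to unscored failures, not how many there will be.

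**5. Direction**

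Under Inclusion Criteria, LSTR teeth enter because resorption beyond two thirds rules out pulpectomy. Control teeth must have no pathological resorption, and any physiological resorption must not exceed two thirds. That difference probably works against LSTR, whereas antibiotics in the LSTR arm alone would work for it. The documents do not allow the two to be netted. Antibiotic use could also differ between arms under an identical rule, which is a further reason to record it by arm.

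**The case against.** The strongest case on the other side has five parts.

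- **Timing.** The sentence closes a procedural paragraph, and follow-up is described separately. Its natural reading is a prescription at the treatment visit. A reader might infer that LSTR failures will be masked during follow-up; the text shows only that they could be. This stands.
- **Trigger.** The wording joins swelling and lymphadenopathy, so it does not say that any swelling leads to antibiotics. This stands and narrows the number of teeth affected, but the asymmetry remains.
- **Control arm.** A reader might infer a comparison of paste plus antibiotic with pulpectomy alone. The control paragraph is brief throughout, omitting for example the rubber dam and the irrigants, so its silence is weak evidence of a different policy. Antibiotic allergy is excluded in both groups, which is compatible with antibiotics being possible in either. This also stands: silence does not show that control children receive none. It does not remove the fact that a stated rule appears in one arm only.
- **Confounding by indication.** The arms differ in disease at entry, so correcting this point alone would not make them comparable. True, and it is why no net direction is claimed.
- **Exclusion analysis.** Dropping teeth given antibiotics at the treatment visit could remove the most acute cases from one arm only. This stands, and such an analysis is not recommended.

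**Conclusion.** The point holds in a limited form. The plan writes a systemic co-intervention into one arm, aims it partly at a scored sign, leaves its timing open, and provides neither recording nor an analysis rule. This is more than missing detail, because the stated procedures differ by arm on something that bears on a named effectiveness criterion.

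A reader might go further and conclude that LSTR success will be overstated by some number of points. The documents do not support that. They give no failure rate, no rate of antibiotic use and no share of failures that would go unscored, and the illustration runs from zero to 10 points depending wholly on those assumptions. The net direction is uncertain because of the difference in resorption at entry. The conclusion assumes only that the arm descriptions are followed as written; if practice is in fact the same in both arms, a sentence saying so removes the asymmetry but not the need for recording and a scoring rule.

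**What to change.** 1. **Reconcile the arm descriptions.** The LSTR and pulpectomy paragraphs should state whether the provision applies to both arms and at what time. Which clinical rule is used is for the sponsor and investigators; none is proposed here.
2. **Record use.** For every tooth in both arms, record any systemic antibiotic with date, reason, and whether it was given at treatment or during follow-up. Report use by arm.
3. **Pre-specify one scoring rule for both arms.** A tooth with new or recurrent swelling after treatment that led to systemic antibiotics is scored as a clinical failure from that date, even if the swelling has resolved by the next visit. The rule belongs in the failure definition that the survival analysis needs in any case.
4. **Treatment-visit use.** Report results by antibiotic use at the treatment visit as descriptive only, not as an exclusion analysis.

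**Cost.** One case-report field and a few lines of SAP text. Clinical success may be slightly lower. If the provision remains confined to LSTR, the scoring rule can act only in that arm, and the report should say so.
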